Subjects who are withdrawn from the open-label treatment period will taper YKP3089 according to the schedule described in [Table 10](#), unless for safety reasons the investigator judges it necessary to discontinue study drug immediately. For subjects taking phenytoin or phenobarbital, discontinuing YKP3089 may reduce the plasma concentration of these AEDs. Doses of phenytoin or phenobarbital may need to be adjusted as clinically indicated.

Table 10. Study Drug Taper Schedule for Subjects Completing Open-Label Treatment

Final open-label dose of YKP3089 (mg/day)	YKP3089 Dose During Taper (mg/day)		
	Week 1	Week 2	Week 3
50 or 100	None		
150 or 200	100	None	None
250 or 300	200	100	None
350 or 400	300	200	100

The follow up visit will take place 14 days after the subject's last dose, following taper and discontinuation of YKP3089; at any time during the open-label treatment; or after 12 months of open-label treatment if there is no additional treatment beyond that point.

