- Administer C-SSRS (Since Last Visit version)
- Perform urine pregnancy test (for female subjects of child-bearing potential)
- Draw blood for laboratory safety assessment
- Record concomitant medications
- Perform drug accountability
- Record AEs
- Dispense study drug as instructed by IWRS
- Schedule a return to occur in 8-9 weeks for Visit 13

9.1.13 *Visit 13, Day 263*

As shown in [Table 1](#), the following will be performed at Visit 13:

- Record vital signs
- Conduct brief neurologic exam if required
- Administer C-SSRS (Since Last Visit version)
- Perform urine pregnancy test (for female subjects of child-bearing potential)
- Draw blood for laboratory safety assessment
- Record concomitant medications
- Perform drug accountability
- Record AEs
- Dispense study drug as instructed by IWRS.
- Schedule a return to occur in 14-15 weeks for Visit 14

9.1.14 *Visit 14 or Termination from study—Taper Visit*

As shown in [Table 1](#), the following will be performed at Visit 14 or at the time of early termination from the study.

- Record vital signs
- Measure weight
- Conduct full physical examination
- Conduct full neurologic examination
- Administer C-SSRS (Since Last Visit version)
- Perform 12-lead ECG once
- Perform urine pregnancy test (for female subjects of childbearing potential)
- Draw blood for laboratory safety assessment
- Obtain urine for urinalysis
- Record concomitant medications
- Perform drug accountability
- Record AEs
- For subjects who completed 1 year of open-label treatment, determine whether the subject is benefitting from open-label treatment with YKP3089

For subjects who are benefitting from open-label treatment:

- Dispense open-label medication
- Schedule a return to occur in 3 months for next visit
- See section [9.1.16](#) for further instructions

For subjects who are not benefitting from open-label treatment or leaving the open-label treatment due to any reasons at any time:

- Dispense taper open-label study drug bottles as instructed by IWRS if needed
- Schedule a return to occur in 2 weeks of the last dose for Visit 15 if tapered
- Schedule a return to occur in 2 weeks for Visit 15 if not tapered

9.1.15 *Visit 15, End of Study Follow-up (14 days from the last dose)*

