6 STUDY DESIGN AND VISIT SCHEDULE

This is a multicenter, open label study in subjects with poorly controlled partial seizures. The study will consist of a:

- screening period,
- open-label titration phase,
- open label maintenance phase
- taper and follow up.

The study will enroll:

- Subjects on stable doses of phenytoin
- Subjects on stable doses of phenobarbital
- Subjects on stable doses of other concomitant AEDs

from approximately 80-110 sites (US and other countries)t

At least 20 subjects taking phenytoin and at least 20 subjects taking phenobarbital are to be enrolled. Additional subjects taking AEDs other than phenytoin or phenobarbital are to be enrolled in order to expose at least 1,000 subjects for 6 months to further evaluate long term safety.

Details about inclusion / exclusion criteria are included in Protocol Sections 7.3 and 7.4.

The screening period for subjects on stable doses of phenytoin or stable doses of phenobarbital or stable doses of other concomitant AEDs will be up to 21 days.

The open label treatment period will consist of a 12 week titration phase followed by an open label maintenance phase.

The titration phase for subjects on stable doses of phenytoin or stable doses of phenobarbital will be 12 weeks. During the 12-week up-titration phase, subjects will increase YKP3089 dose every 2 weeks to a target dose of 200 mg/day as described in the table below:

Table 1. YKP3089 Initial Up-Titration for subjects on phenytoin and phenobarbital

YKP3089 dose (mg/day)					
Week 1 & 2	Week 3 & 4	Week 5 & 6	Week 7 & 8	Week 9 & 10	Week 11 & 12
12.5	25	50	100	150	200

The titration phase for subjects on stable doses of other concomitant AEDs will be 12 weeks. Increasing doses of YKP3089 will be administered (50, 100, 150 and 200 mg/day) at 2-week intervals as described in the table below:

Table 2. YKP3089 Initial Up-Titration for subjects on concomitant AEDs other than phenytoin or phenobarbital

YKP3089 dose (mg/day)					
Week 1 & 2	Week 3 & 4	Week 5 & 6	Week 7 & 8	Week 9 & 10	Week 11 & 12
12.5	25	50	100	150	200

During titration phase, the investigator may add, remove, or adjust the dosage of any concomitant AEDs, as clinically indicated:

Table 3. Dose Adjustment Rules during Titration Phase

Cohort →	Subjects taking Phenytoin or Phenobarbital	Subjects taking AEDs other than Phenytoin or Phenobarbital
Adjustments of any Concomitant AEDs	Not Allowed	Allowed
Adjustments of YKP3089	Not Allowed	Allowed

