Adjustment of Phenytoin or Phenobarbital	Allowed	Not Applicable

Monotherapy with YKP3089 will not be allowed. If clinically indicated, titration can be stopped below 200 mg/day. A minimum dose of 50 mg/day is necessary to continue in the study.

During open label maintenance phase:

- (1) For subjects taking phenytoin or phenobarbital, the initial target dose will be 200 mg/day. If the investigator feels that a subject requires a dose that is higher than 200 mg/day, the dose can be increased to a maximum of 400 mg/day once the target dose of 200 mg/day was reached. The upward dose adjustments should occur every other week in increments of 50-mg/day. If the investigator feels that a subject requires a dose that is lower than 200 mg/day, the dose can be reduced to a minimum of 50 mg/day once the target dose of 200 mg/day was reached. The downward dose adjustments may occur weekly by 100 mg/day or 50 mg/day.
- (2) For subjects taking other concomitant AEDs, the initial target dose will be 200 mg/day. If the investigator feels that a subject requires a dose that is higher than 200 mg/day, the dose can be increased to a maximum of 400 mg/day once the target dose of 200 mg/day was reached. The upward dose adjustments should occur every other week in increments of 50 mg/day. If the investigator feels that a subject requires a dose that is lower than 200 mg/day, the dose can be reduced to a minimum of 50 mg/day once the target dose of 200 mg/day was reached. The downward dose adjustments may occur weekly by 100 mg/day or 50 mg/day.
- (3) The investigator may add (except phenytoin or phenobarbital), remove, or adjust the dosage of any concomitant AEDs, as clinically indicated:

Table 4. Dose Adjustment Rules during Maintenance Phase

Cohort →	Subjects taking Phenytoin or Phenobarbital	Subjects taking AEDs other than Phenytoin or Phenobarbital
Adjustments of any Concomitant AEDs	Allowed	Allowed
Adjustments of YKP3089	Allowed	Allowed
Adjustment of Phenytoin or Phenobarbital	Allowed	Not Applicable

Subjects who are withdrawn from the open-label treatment period will taper YKP3089 according to the schedule described in [Table 5](#), unless for safety reasons the investigator judges it necessary to discontinue study drug immediately.

Table 5. Study Drug Taper Schedule for Subjects Completing Open-Label Treatment

Final open-label dose of YKP3089 (mg/day)	YKP3089 Dose During Taper (mg/day)		
	Week 1	Week 2	Week 3
50 or 100	None		
150 or 200	100	None	None

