250 or 300	200	100	None
350 or 400	300	200	100

Details about scheduled procedures during titration phase, open label maintenance phase and taper follow-up are included in Protocol Section 6.1.2.1.

Study schedule and assessments flow chart is included in [Appendix 1](#).

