11.4.1 Exposure to YKP3089 study drug

The following will be summarized overall and by safety evaluable subgroups:

- Length of exposure (weeks and months)
- Number and percentages of subjects by time intervals (0-<1 weeks, 1-<2 weeks, 2-<4 weeks, 4 - <12 weeks, 12 - <24 weeks, 24-<48 weeks, 48-<96 weeks, >=96 weeks)
- Number and percentage of subjects by exposure categories: >= 1 dose, >=6 months, >=12 months, >=18 months, >=24 months, >=36 months

For any interim reporting of the results from this study, only applicable exposure categories based on maximum duration of exposure observed will be included in the summary tables).

Derivation for length of exposure to YKP3089:

- Length of exposure to YKP3089 (days) = (stop date – start date + 1).
- Length of exposure to YKP3089 (weeks) = length of exposure to YKP3089 (days)/7
- Length of exposure to YKP3089 (months) = length of exposure to YKP3089 (days)/30.4

Start and stop dates are define as per rules below:

Analysis Period	Subject Participation	
	Enrolled and discontinued study	Enrolled and ongoing at date of data cut-off
Overall	Start Date = First dose date Stop Date = last dose date	Start date = First dose date Stop Date = date of data cut-off
Titration Phase	Start date = First dose date Stop Date = Visit 9 date OR Last dose date	Start date = First dose date Stop Date = Visit 9 date OR date of data cut-off
Maintenance Phase	Start Date = Visit 9 date + 1 Stop Date = Last dose date	Start Date = Visit 9 date + 1 Stop Date = date of data cut-off

Descriptive statistics (mean, standard deviation, median, minimum, and maximum) will be provided to summarize the length of exposure (in weeks and in months) for each safety evaluable subgroup and overall. Similar summary results will be prepared by modal dose within each safety evaluable subgroup.

The number and percentage of subjects at each dose level will be summarized by safety evaluable subgroup and overall for the titration phase, the maintenance phase and overall during study. The length of exposure to YKP3089 at each dose level (from 12.5 mg up to maximum daily dose reported in study) will be summarized using descriptive statistics (mean, standard deviation, median, minimum, and maximum).

Dosing duration will also be expressed in terms of total subject years of exposure to YKP3089, calculated as the sum of all subject exposure days, divided by 365.25.

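### SAP 11.4.1 has no taper period and ends maintenance at the last dose, so taper days count as maintenance for subjects who discontinue and taper, while SAP 8 and 11.4 end maintenance at Visit 14

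*SAP*

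**What the plan says.** SAP 6 divides the study into screening, titration, maintenance and "taper and follow up", and Protocol 6.1 does the same. The exposure table in SAP 11.4.1 has only three rows: Overall, Titration Phase and Maintenance Phase. For a subject who has discontinued, maintenance is "Start Date = Visit 9 date + 1 Stop Date = Last dose date". Titration ends at Visit 9 or at the last dose.

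The protocol places the last dose after taper. Section 6.1.2.3 says "The follow up visit will take place 14 days after the subject's last dose, following taper and discontinuation of YKP3089". Section 9.1.14 has taper drug dispensed at Visit 14 or the Termination Visit, and then "Schedule a return to occur in 2 weeks of the last dose for Visit 15 if tapered".

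On who tapers, SAP 6 says "Subjects who are withdrawn from the open-label treatment period will taper YKP3089 according to the schedule described in" its Table 5, with an exception for immediate stops for safety reasons. Two rows of that table read "150 or 200 100 None None" and "350 or 400 300 200 100", by week. Final doses of 50 or 100 mg have no taper.

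The affected output is in SAP 11.4.1: "The number and percentage of subjects at each dose level will be summarized by safety evaluable subgroup" and overall, for titration, maintenance and the whole study. SAP 11.4 also derives days at each dose level by phase.

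SAP 8 describes maintenance as Visit 9 to Visit 14, and SAP 11.4 uses the same span for modal dose.

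**The concern.** The SAP gives two ends for the same phase, and the only one written as a date rule takes in the taper. Two programmers working from SAP 11.4 and SAP 11.4.1 could produce different maintenance tables.

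The low-dose rows are where this matters. A subject may be at 100 mg in maintenance because the dose was reduced or because titration stopped there. A reader of a long-term safety study would use that row to see how many subjects were maintained at 100 mg, and for how long. Under the SAP 11.4.1 dates, the row can also hold subjects whose only maintenance time at 100 mg was an exit week. No minimum duration applies, and nothing in the SAP removes taper days.

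**Working it through.** The plan states no figure to reproduce. SAP 9.1 says that no formal sample size estimation was made. The check is a day count from the SAP's own formula and taper table.

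**1. Taper days by final dose** (SAP 6, Table 5; weeks × 7)

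| Final dose (mg/day) | Taper weeks at (mg) | Days added | Of which at 100 mg |
|---|---|---|---|
| 50 or 100 | none | 0 | 0 |
| 150 or 200 | 100 | 7 | 7 |
| 250 or 300 | 200, 100 | 14 | 7 |
| 350 or 400 | 300, 200, 100 | 21 | 7 |

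**2. Maintenance length for one leaver.** SAP 11.4.1: length = stop − start + 1. With Visit 9 at its target, Day 99, the start is Day 100.

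- Leaving at Day 365, stop at the Termination Visit: 365 − 100 + 1 = 266 days. Stop at the last taper dose: 266 + 7 = 273, 266 + 14 = 280 or 266 + 21 = 287. The taper share is 7/273 = 2.6% to 21/287 = 7.3%.
- Leaving at Day 113 from 200 mg: 113 − 100 + 1 = 14 days without taper and 14 + 7 = 21 with it. The taper share is 7/21 = 33%.

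The effect on duration is small for long stayers and larger for early leavers.

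**3. The maintenance 100 mg row.** This needs rates that the documents do not give. Assumptions, per 1,000 subjects entering maintenance:

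- 5-30% later taper from 150 mg or more;
- 2-10% are truly treated at 100 mg, for 180 days each;
- the two groups do not overlap.

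With T tapering and G truly at 100 mg, the taper-only share is T/(T + G) and the mean is (7T + 180G)/(T + G).

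| T | G | Row n | Taper-only share | Mean days | Median days |
|---|---|---|---|---|---|
| 50 | 100 | 150 | 50/150 = 33% | (350 + 18,000)/150 = 122.3 | 180 |
| 50 | 50 | 100 | 50/100 = 50% | (350 + 9,000)/100 = 93.5 | 93.5 |
| 200 | 50 | 250 | 200/250 = 80% | (1,400 + 9,000)/250 = 41.6 | 7 |
| 300 | 20 | 320 | 300/320 = 94% | (2,100 + 3,600)/320 = 17.8 | 7 |

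Without taper days, both the mean and the median would be 180. The median becomes 7 only when T exceeds G.

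**4. Leavers before Visit 9.** Titration then stops at the last dose, so the same rule puts taper days into titration. On the scheduled titration, a subject at 150 or 200 mg has already spent two weeks at 100 mg. The taper therefore adds 7 days to that subject's 100 mg time and does not bring a new subject into the row.

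**The case against.** The strongest reply is that SAP 8 and SAP 11.4 already end maintenance at Visit 14. For anyone leaving at or before that visit, this is before taper. The SAP 11.4.1 dates are introduced as a derivation of exposure length, and the SAP never says that they also drive the dose-level counts. This stands in part: inclusion of taper days in the dose-level rows follows from the only date rule given by phase, not from an explicit instruction. But the Visit 9 to Visit 14 span in SAP 11.4 is attached to modal dose alone. If taper was never meant to count, the SAP 11.4.1 wording still needs correcting.

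A reader might infer that every leaver from 150 mg or more adds a week at 100 mg. The documents do not support that. Subjects stopped immediately for safety do not taper (SAP 6; Protocol 6.1.2.3), and Protocol 9.3 requires an immediate stop for rash or other hypersensitivity symptoms whose cause cannot be determined. Subjects lost to follow-up may never start a taper. Subjects finishing on 50 or 100 mg, and those still on treatment before taper at data cut-off, add no taper days.

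The consequence is also limited. The analysis is descriptive (SAP 10.1), and adverse event incidence uses subjects, not maintenance days, as its denominator (SAP 13.1). By-subject exposure listings are planned. The table shells are in separate documents that were not available here.

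**Conclusion.** The point holds as an inconsistent definition of the end of maintenance, with no taper period in the exposure table. Followed as written, SAP 11.4.1 counts 7, 14 or 21 taper days as maintenance for subjects who discontinue after Visit 9 and actually taper, always including a week at 100 mg. For leavers before Visit 9, the taper days go into titration.

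The mechanism rests on the text; the size does not. It is tempting to say that leavers fill the 100 mg row, but the documents give neither the taper rate nor the number maintained at 100 mg. Over the assumed ranges the taper-only share runs from about 33% to 94%, and at the low end the median stays at 180 days.

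It would also be wrong to conclude that the exposure reporting as a whole is distorted. Overall exposure and subject-years properly run to the last dose, and modal dose as worded excludes taper. The fault lies in the phase-specific durations and dose-level rows. It affects description, not inference, and is worth correcting because the correction is cheap.

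**What to change.** This changes the analysis only; the taper schedule is untouched.

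- In SAP 11.4.1, define the end of titration or maintenance once. For subjects who discontinue, use the last dose before taper starts, taken from the eCRF dose dates (Protocol 8.2.1.2 has exact dates and doses recorded at each visit).
- If that date cannot be identified, use the Termination Visit date. Use the Visit 14 date only for subjects who stop at Visit 14. A general Visit 14 cut would discard treatment beyond year one, since subjects who continue leave later through the Termination Visit (Protocol 9.1.16).
- Add a Taper row from the next day to the last dose date.
- Exclude taper days from the titration and maintenance duration and dose-level tables. Keep them in overall exposure.
- Align SAP 8 and the modal-dose definition in SAP 11.4 with the new end date. For subjects who continue past year one, this extends the modal-dose window beyond Visit 14. If a year-one window is wanted there, label it as such.

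The cost is SAP wording and one extra derived date. The documents describe no taper-start field, so the rule for finding that date must be written down. Reported maintenance durations become up to three weeks shorter for subjects who taper.

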11.4.2 Phenytoin and Phenobarbital Dosing during Titration Phase

A by-subject data listing including phenytoin and phenobarbital dosing starting with baseline records up to an including end of titration (Visit 9) or early discontinuation for subjects who discontinue before Visit 9 will be prepared

separately for the two safety evaluable subgroups: subjects taking phenytoin and YKP3089, subjects taking phenobarbital and YKP3089, respectively.

Daily dose of phenytoin/phenobarbital will be computed using frequency and dose as recorded on eCRF: total daily dose (mg) = dose (mg) x frequency.

At each visit post-baseline during titration phase (ie, for visits up to and including Visit 9) change in phenytoin/phenobarbital total daily dose will be assessed for each subject based on comparison to the daily dose at the previous visit. The following variables will be derived:

1. Change from previous visit total daily dose of phenytoin/phenobarbital = total daily dose at current visit – total daily dose at the previous visit.
2. Change in total daily dose of phenytoin/phenobarbital categories:
 - no change, if total daily dose at current visit – total daily dose at the previous visit = 0.0
 - increase, if total daily dose at current visit – total daily dose at the previous visit > 0.0
 - decrease, if total daily dose at current visit – total daily dose at the previous visit < 0.0
3. Change from baseline total daily dose of phenytoin/phenobarbital = total daily dose at current visit – total daily dose at baseline.
4. Percent change from previous visit total daily dose of phenytoin/phenobarbital = [(total daily dose at current visit – total daily dose at the previous visit)/(total daily dose at the previous visit)] x 100. Note: percent change will have negative values if the change represents a decrease, positive values if the change represents an increase and will be 0% if there is no change.
5. Percent change from baseline total daily dose of phenytoin/phenobarbital = [(total daily dose at current visit – total daily dose at the baseline)/(total daily dose at the baseline)] x 100. Note: percent change will have negative values if the change represents a decrease, positive values if the change represents an increase and will be 0% if there is no change

Using baseline and end of titration phase total daily dose phenytoin/phenobarbital, the following variables will be derived:

- Change from baseline to end of titration phase (Visit 9 or early discontinuation, whichever is earlier) will be computed as (total daily dose of phenytoin/phenobarbital at the end of titration – baseline total daily dose of phenytoin/phenobarbital).
6. Change in total daily dose of phenytoin/phenobarbital categories:
- no change, if total daily dose at end of titration phase – total daily dose at baseline = 0.0
 - increase, if total daily dose at end of titration phase – total daily dose at baseline > 0.0
 - decrease, if total daily dose at end of titration phase – total daily dose at baseline < 0.0
- Percent change from baseline to end of titration phase (Visit 9 or early discontinuation, whichever is earlier) will be computed as [(total daily dose of phenytoin/phenobarbital at the end of titration – baseline total daily dose of phenytoin/phenobarbital)/ baseline total daily dose of phenytoin/phenobarbital] x 100.

The following summary results will be prepared for the two safety evaluable subgroups: subjects taking phenytoin and YKP3089, subjects taking phenobarbital and YKP3089, respectively:

- Summary statistics (n, mean, SD, standard error, median, minimum, maximum) for :
 - baseline total daily dose of phenytoin/phenobarbital
 - end of titration phase total daily dose of phenytoin/phenobarbital
 - change from baseline to end of titration in total daily dose of phenytoin/phenobarbital
 - increase from baseline to end of titration in total daily dose of phenytoin/phenobarbital (including only subjects with an increase in total daily dose of phenytoin/phenobarbital)
 - decrease from baseline to end of titration in total daily dose of phenytoin/phenobarbital (including only subjects with a decrease in total daily dose of phenytoin/phenobarbital)

- percent change from baseline to end of titration in total daily dose of phenytoin/phenobarbital
- total daily dose of phenytoin/phenobarbital by post-baseline visit.
- change from previous visit total daily dose of phenytoin/phenobarbital (reported by visit)
- increase from previous visit total daily dose of phenytoin/phenobarbital (reported by visit and including only subjects with an increase in total daily dose of phenytoin/phenobarbital for the respective visit)
- decrease from previous visit total daily dose of phenytoin/phenobarbital (reported by visit and including only subjects with a decrease in total daily dose of phenytoin/phenobarbital for the respective visit)
- percent change from previous visit total daily dose of phenytoin/phenobarbital (reported by visit)
- change from baseline total daily dose of phenytoin/phenobarbital (reported by visit)
- percent change from baseline total daily dose of phenytoin/phenobarbital (reported by visit)
- Number and percentage of subjects:
 - no change from baseline to end of titration phase in total daily dose of phenytoin/phenobarbital
 - increase from baseline to end of titration phase in total daily dose of phenytoin/phenobarbital
 - decrease from baseline to end of titration phase in total daily dose of phenytoin/phenobarbital
 - reporting “no change from previous visit” during titration phase (ie, subjects with “no change” in total daily dose of phenytoin/phenobarbital for all post-baseline visits).

- reporting at least one increase in total daily dose during titration phase (ie, subjects with at least one “increase” in total daily dose of phenytoin/phenobarbital for all post-baseline visits).
- reporting at least one decrease in total daily dose during titration phase (ie, subjects with at least one “decrease” in total daily dose of phenytoin/phenobarbital for all post-baseline visits).
- reporting decreases in total daily dose during titration phase: by number of decreases (1, 2, 3, >3)
- Plots by visit for percent change from baseline in total daily dose of phenytoin/phenobarbital to each post-baseline visits during titration phase
- Plots by visit for observed mean total daily dose of phenytoin/phenobarbital

